4.1.5.2. Estimand Strategy for Binary Endpoints

Evaluation of non-inferiority as well as superiority for LEO 90100 versus Daivobet® ointment will be based on the Wald-type test statistic for the estimated treatment effect from a logistic regression model, adjusted for baseline PGA.

The main analysis is based on the following assumptions:

1. Missing data will be handled according to [Table 4-1](#).
2. Use of prohibited medication and procedures will be assumed to have no influence on the endpoint of interest among subjects not discontinuing IMP.

For each of the imputed datasets, estimates of the treatment effect along with the associated standard errors will be kept on the log-scale. The pooled estimate of risk difference and OR at Week 4, along with the associated 95% CIs and nominal p-values will be presented based on applying Rubin's rules to the estimates and standard errors from the logistic regression of the imputed data sets and transforming to the odds-scale.

The logistic regression will include both baseline PGA and the baseline score value of the endpoint (eg, continuous mPASI, [CCI](#) category) for binary endpoints other than PGA.

Primary Analysis of the Primary Estimand

The purpose of 'hypothetical' strategy is to predict what value the estimands variable would take if the given subject would not permanently discontinue IMP due to pandemic restrictions, assuming a similar course of events as experienced by subjects from the same treatment arm who have not permanently discontinued IMP due to pandemic restrictions. With this purpose in mind 2 questions naturally arise because of the composite strategy used to address permanent discontinuation of IMP independent of pandemic restrictions:

1. Would the subject still have been on treatment at Week 4 as opposed to having permanently discontinued IMP independently of pandemic restrictions beforehand?
2. If yes, would the subject have had binary response (0/1) with a 2-point reduction from baseline at Week 4?

In practice, both of these hypothetical questions will be addressed, although in reverse order, by carrying out the following steps:

1. Under missing at random (MAR) assumption within treatment arm, binary response at Week 4 (or Week 2) will be imputed for subjects who have permanently discontinued IMP due to pandemic restrictions prior to Week 4 (or Week 2) and for subjects who have not permanently discontinued IMP prior to Week 4 (or Week 2) and whose score at Week 4 (or Week 2) is missing due to pandemic restrictions. Fully conditional specification (FCS) method will be implemented to impute missing binary responses by implementing logistic or regression methods (number of imputed datasets = 1000; seed = 2)[3]. FCS logistic regression will be implemented for the binary PGA and ~~CCI~~ endpoints. FCS linear regression will be utilised to impute the mPASI score. Binary mPASI-75 and mPASI-90 will be derived from the imputed score. Response at Week 4 (or Week 2) will be imputed using the stratification PGA, the value baseline score value (not for PGA as it coincides with the randomisation strata) and response at the Week 2 visit (not applicable when imputing data for Week 2) as covariates.
2. Non-responder imputation will be applied for subjects who have not permanently discontinued IMP prior to Week 4 (or Week 2) and whose binary response at Week 4 (or Week 2) is missing for reasons other than pandemic restrictions.
3. A logistic regression model will be implemented to estimate each subject's probability of permanent discontinuation of IMP not due to pandemic restrictions up until Week 4 (Day 29) among subjects who permanently discontinued IMP due to pandemic restrictions. Stratification PGA, sex and age will be utilised as covariates. Using the subject predicted probability (p_i) of discontinuation, the following steps will be followed to derive the treatment adherence variable:
 - a. For each imputed dataset, a value from the exponential distribution with rate p_i will be drawn and multiplied with 29 to obtain days (starting seed = 3)
 - b. Person-days already spent in the trial will be added to the drawn number
 - c. Derive the treatment adherence variable with the following categorisation:
 - Days < 15 : subject discontinued before Week 2
 - $15 \leq \text{Days} < 29$: subject discontinued after Week 2 and before Week 4
 - $\text{Days} \geq 29$: the subject did not discontinue.

d. For subjects predicted to be discontinued before Week 2 or Week 4, non-responder imputation will be applied to the visits after the predicted discontinuation.

Table 4–2 Hypothetical Strategy for Addressing Permanent Discontinuation of IMP Due to Pandemic Restrictions and Handling of Missing Data in the Primary Analysis of the Primary Estimand

Step no.	Description	Subjects in scope for imputation	Purpose
1	Impute binary (0/1) response at Week 4 under MAR assumptions within treatment arm	Subjects who have permanently discontinued IMP due to pandemic restrictions prior to Week 4.	Hypothetical strategy
		Subjects who have not permanently discontinued IMP prior to Week 4 and whose score at Week 4 is missing due to pandemic restrictions.	Handling of missing data
2	Impute binary (0/1) response at Week 4 based on NRI	Subjects who have not permanently discontinued IMP prior to Week 4 and whose score at Week 4 is missing for reasons other than pandemic restrictions.	Handling of missing data
3	Impute treatment adherence status at Week 4 within treatment arm	Subjects who have permanently discontinued IMP due to pandemic restrictions prior to Week 4.	Hypothetical strategy

Abbreviations: IMP=investigational medicinal product; MAR=missing at random; NRI=non-responder imputation.

Sensitivity Analysis of the Primary Estimand

For the sensitivity analysis, which is rather conservative against the LEO 90100 group, observed data at Week 4 will be used in the Daivobet® ointment group for the subjects who permanently discontinued IMP not due to pandemic restrictions. In addition, missing data for subjects in the Daivobet® ointment group will be imputed, as described in Point 1 of hypothetical strategy summarised in [Table 4–2](#).

Primary Analysis of the Secondary Estimand

For the primary analysis of the secondary estimand, under MAR assumption within treatment arm, binary response at Week 4 will be imputed for subjects who have permanently discontinued IMP due to pandemic restrictions prior to Week 4 and for subjects who have not permanently

discontinued IMP prior to Week 4 and whose score at Week 4 is missing due to pandemic restrictions. FCS method will be applied, as described for the primary analysis of the primary estimand.

4.1.5.3. Estimand Strategy for Continuous Endpoints

With the treatment policy strategy, subjects who have permanently discontinued IMP independently of pandemic restrictions prior to the endpoint Visit 4 (Week 4) will be included in the analysis with the actually observed score at this Visit.

Permanent discontinuation of IMP due to pandemic restrictions will be addressed by a hypothetical strategy. Data collected after such an event will not be applied in the analysis. The hypothetical scenario envisaged is that permanent discontinuation of IMP due to pandemic restrictions would not occur, assuming subjects who have experienced this event would respond like subjects from the same treatment arm who have not experienced it. The hypothetical strategy and the handling of missing data in the primary analysis are outlined in [Table 4-3](#).

Table 4-3 Hypothetical Strategy for Addressing Permanent Discontinuation of IMP Due to Pandemic Restrictions and Handling of Missing Data in the Primary Analysis of the Primary Estimand for Continuous Secondary Endpoints

Step no.	Description	Subjects in scope for imputation	Purpose
1	Impute score at the endpoint visit under MAR assumptions within treatment arm	Subjects who have permanently discontinued IMP due to pandemic restrictions prior to the endpoint visit.	Hypothetical strategy
		Subjects who have not permanently discontinued IMP due to pandemic restrictions prior to the endpoint visit and whose score at the endpoint visit is missing.	Handling of missing data

Abbreviations: IMP=investigational medicinal product; MAR=missing at random.

The imputation of scores will be carried out like the imputation of mPASI scores for the primary estimand of the primary endpoint (FCS linear regression with stratification PGA, value of the continuous variable at baseline and Week 2 as covariates). Data collected from subjects who have permanently discontinued IMP independently of pandemic restrictions will be included when applying this multiple imputation method (see [Appendix 6.3.2.1](#)), in alignment with the treatment policy strategy used for addressing occurrences of that IE.

Project Document Version No.: 2.0; Document Effective Date: 29Mar2024

TP-GDO-WW-016-09

Effective Date: 22 Dec 21

Related to: SOP-GDO-WW-019

Page 24 of 51

Each of the imputed data sets will be analysed based on an analysis of covariance (ANCOVA) model, including treatment arm, and adjusting for the stratification PGA and baseline score as covariates. The pooled estimate of the difference in the least-square (LS)-mean change from baseline at Week 4, along with the associated 95% CIs and nominal p-values will be presented based on applying Rubin's rules to the estimates and standard errors from the ANCOVA analyses of the imputed data sets.

4.2. Primary Endpoint Analysis

4.2.1. Definition of Endpoint(s)

The primary endpoint is having PGA score of 0 (clear) or 1 (almost clear) at Day 29, with at least a 2-point reduction from baseline.

4.2.2. Analytical Approach

The primary endpoint will be analysed following the estimand strategy for binary endpoints described in Section 4.1.5.1 and Section 4.1.5.2, including a primary and a sensitivity analysis of the primary estimand, and a primary analysis on the secondary estimand.

The non-inferiority and superiority 2-sided hypothesis, described in Section 2, will be tested for LEO 90100 vs Daivobet® ointment based on the primary analysis for the primary estimand.

A summary of PGA by visit will be provided by treatment group and overall.

A by-subject listing for PGA data will also be provided.

4.3. Secondary Endpoint Analysis

4.3.1. Key Secondary Endpoint

4.3.1.1. Definition of Endpoint(s)

The key secondary endpoint is having a decrease in mPASI of at least 75% (mPASI-75) from baseline to Day 29.

4.3.1.2. Analytical Approach

The binary key secondary endpoint will be analysed following the estimand strategy for binary endpoints described in Section 4.1.5.1 and Section 4.1.5.2. The superiority 2-sided hypothesis, described in Section 2, will be tested for LEO 90100 vs Daivobet® ointment based on the primary analysis for the primary estimand.

4.3.2. Secondary Endpoint

The secondary endpoint is having a decrease in mPASI of at least 90% (mPASI-90) from baseline to Day 29.

The planned analysis on the secondary endpoint is the same as the key secondary endpoint (mPASI-75) as described in Section 4.3.1.

4.4. CCI [REDACTED]

CCI [REDACTED] include:

CCI [REDACTED] related to primary objective:

- CCI [REDACTED]

The binary CCI [REDACTED] will be analysed following the primary estimand strategy for binary endpoints described in Section 4.1.5.1 and Section 4.1.5.2. The continuous CCI [REDACTED] CCI [REDACTED] will be analysed following the estimand strategy for the continuous endpoints, as per Section 4.1.5.3.

A summary of the change from baseline in continuous variables (mPASI, CCI [REDACTED]) will be provided by visit, by treatment group and overall, for observed values.

Observed proportions of categorical variables **CCI** will be summarized by visit, by treatment group and overall.

By-subject listing will be provided for data on mPASI, **CCI** score.

4.5. Safety Analyses

All safety analyses will be made on the safety analysis set.

4.5.1. Extent of Exposure

The duration of exposure to IMP in a specific week interval will be calculated as the number of days from date of first IMP administration in that period to the date of last IMP administration in that period, both days included.

Exposure to IMP will be presented as days and weeks of exposure.

Patient years of exposure is the duration of exposure to IMP in years:

Patient years of exposure (years) = (date of last IMP administration – date of first IMP administration + 1)/365.25

Patient years of observation is the duration of observation in years:

Patient years of observation (years) = (date of end of study – date of first IMP administration + 1)/365.25

The total amount of IMP used (g) by each visit interval is collected in the eCRF.

The total amount of IMP used (g) during the total treatment period will be calculated as the sum up of IMP used per visit. If the amount of IMP used is missing for any performed visit, the total amount of IMP used during the total treatment period will be set to missing.

The average weekly amount of IMP used (g) will be calculated as total amount of IMP/duration of exposure \times 7.

The following summaries will be presented for each treatment group:

- Exposure to IMP (days/weeks of exposure to IMP) during the total treatment period.

- Total exposure to IMP (weeks) for all subjects during the total treatment period.
- Patient years of exposure and patient years of observation.
- Total patient years of exposure and patient years of observation for all subjects.
- The average weekly and total amount of IMP used (g) by each visit interval and the total treatment period.
- Number and percent of subjects with overdose (any dose of study drug used greater than 105 g within one week).

By-subject listings will be provided for IMP administration, IMP accountability, and exposure to IMP.

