6.2 Preparation, Handling, Storage and Accountability

Dispensation of IMP

All kits will contain 240 g of IMP.

IMP will be supplied at the dispensing visits listed in the SoA (Table 1–1). Each kit will contain the necessary amount of IMP to treat a subject between 2 visits in the treatment period.

The subject may use up to a maximum of 15 g per day (or 105 g per week), and 240 g of IMP will be dispensed every second week.

Storage of IMP

All LEO Pharma A/S supplied IMP must be stored in a secure, environmentally controlled and monitored (manual or automated) area under the conditions specified on the label and remain in the original container until dispensed, with access limited to the authorised site staff (different from the investigator).

The investigator or designee (e.g., hospital pharmacy) must maintain a log to confirm appropriate conditions (e.g., temperature) have been maintained during transit for all IMP received, and any discrepancies are reported and resolved before use of the IMP. Damaged IMP should be documented and may not be used. Storage facilities should be checked at least every working day.

The following storage conditions and handling precautions should be observed for LEO 90100:

- Store below 30°C. Do not freeze.
- Extremely flammable aerosol.
- Pressurised container: May burst if heated.
- Protect from sunlight.
- Do not expose to temperatures exceeding 50°C.
- Do not pierce or burn, even after use.
- Do not spray on an open flame or other ignition source.
- Keep away from sparks, open flames and other ignition sources.
- No smoking.
- Keep out of the reach of children.

The following storage conditions and handling precautions should be observed for Daivobet® ointment:

- Do not store above 25°C. Do not refrigerate.
- Keep the tube in the outer carton and away from sunlight.
- Keep out of the reach of children.

Only subjects randomised in the study may receive IMP, and only authorised site staff (different from the investigator) may supply, prepare or administer IMP.

Accountability of IMP

The investigator is fully responsible for the IMP accountability, reconciliation and record maintenance (e.g., receipt, reconciliation and final disposition records). However, the aforementioned tasks will be delegated to an un-blinded person as the investigator needs to stay blinded from the IMP type.

Management of IMP may be delegated (e.g., to a hospital pharmacy) as locally applicable.

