Documentation of drug accountability must be kept of the IMP administered to each individual subject in the trial. This documentation must be available during monitoring visits and will be checked by the monitor to verify correct dispensing of the IMP.

The subject will return used, partly used and unused IMP (including packaging material) at the visits specified in the SoA ([Table 1-1](#)).

Returned IMP (used, partly used and unused [including packaging material]) can be stored under condition as described above and must be stored separately from non-allocated IMP.

All unused IMP (including packaging material) supplied by the contract manufacturing organisation (CMO) on behalf of LEO Pharma A/S will be returned to the CMO or local depot. Prior to their return, the IMP must be fully accounted for by the monitor with the help of site staff responsible for dispensing the IMP.

IMP Destruction

Used and unused IMP will be destroyed by the CMO or local depot according to approved procedures and/or local requirements.

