7.1 Discontinuation of Trial Treatment

It may be necessary for a subject to permanently discontinue IMP. If IMP is permanently discontinued, the subject should, if at all possible, remain in the study and attend an early termination visit and a follow-up visit 2 weeks after the last IMP administration. See the SoA ([Table 1–1](#)) for data to be collected at the time of IMP discontinuation and follow-up and for any further evaluations that need to be completed.

IMP must be discontinued permanently in case of the following:

- An AE that, in the opinion of the investigator or medical monitor of the designated CRO, contraindicates further dosing. The decision made by the designated CRO will need to be confirmed by LEO Pharma A/S;
- Evidence of pregnancy;
- Subject decides to discontinue voluntarily;
- Lack of efficacy defined as at least a **CCI** [REDACTED] in mPASI score from baseline until Week 2 or unscheduled visits thereafter and where the investigator sees a need for rescue therapy.

End-of-treatment Form

An end-of-treatment form will be completed in the eCRF for all subjects exposed to IMP when they have had their last IMP administration. This form will also be completed for subjects who permanently discontinue IMP prior to Week 4 and subjects who withdraw from the trial, unless they were never exposed to IMP (see [Table 1–1](#) for early termination assessments).

The date and time of last IMP administration and time of permanent discontinuation of IMP will be recorded on the end-of-treatment form. It will also be recorded if the subject completed the IMP treatment (i.e., did not discontinue IMP prior to Week 4). If not, the primary reason for permanent IMP discontinuation must be recorded in the medical records and on the end-of-treatment form in the eCRF where the following options are available:

- AE;
- Death;
- Lost to follow-up;
- Pregnancy;
- Withdrawal by subject;
- Lack of efficacy;
- Pandemic restrictions as defined in [Section 9.3.5.1](#);
- Other.

If ‘AE’ is selected, the AE in question will be linked to the IMP discontinuation. If ‘other’ is selected as a reason, a specification must be provided in the eCRF.

It will also be recorded whether the IMP discontinuation was related to the COVID-19 pandemic to support the statistical analysis.

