6.2.4. Treatment Compliance

Treatment compliance will be calculated based on the duration and frequency of IMP administration:

Treatment compliance (%) = (Days with once IMP administered/duration of exposure to IMP) ×100,

Duration of exposure to IMP = date of last IMP administration – date of first IMP administration + 1.

Treatment compliance during the total treatment period will be presented for each treatment group for the safety analysis set.

A by-subject listing on treatment compliance will be provided.

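### The weekly amount of IMP is understated for a subject with no IMP-return visit after Visit 3 but a later recorded last-dose date, because total grams are set to missing only for performed visits

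*SAP*

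**What the plan says.** SAP 4.5.1 (Extent of Exposure) builds the total from visit-level amounts: "The total amount of IMP used (g) during the total treatment period will be calculated as the sum up of IMP used per visit". The missing-data rule follows: "If the amount of IMP used is missing for any performed visit, the total amount of IMP used during the total treatment period" is set to missing. The weekly figure is derived from that total: "The average weekly amount of IMP used (g) will be calculated as total amount of IMP/duration of exposure", times 7.

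For the whole treatment period, SAP 6.2.4 (Treatment Compliance) counts duration from first to last application, both days included: "Duration of exposure to IMP = date of last IMP administration" minus the first date, plus 1. The patient-years-of-exposure formula in SAP 4.5.1 uses the same two dates.

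Grams and dates reach the database by different routes.

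- **Grams** depend on kits coming back. Protocol 6.2 states "240 g of IMP will be dispensed every second week", so a second kit goes out at Day 15. It also states "The subject will return used, partly used and unused IMP (including packaging material) at the visits specified in the SoA"; the Return of IMP row in Table 1–1 marks Visits 3, 4, 5 and early termination.
- **The last-dose date** does not depend on kit return. Protocol 7.1 states "The date and time of last IMP administration and time of permanent discontinuation of IMP will be recorded on the end-of-treatment form", and that form is also completed for exposed subjects who withdraw.

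**The concern.** The rule is there to stop a partial sum from passing as a complete total. It looks at whether a visit was performed, not at whether a dispensed kit was accounted for. If no return visit takes place after Visit 3, no performed visit has a missing amount, so the total stays non-missing with only the first interval's grams in it. The denominator can still run into the second interval. Numerator and denominator then describe different periods, and the error always runs downward.

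What is at stake is modest: the descriptive total-period amount, the weekly average derived from it, and the individual values in the by-subject exposure listing. The protocol foresees missed visits, since Sections 7.1 and 7.2 ask for the early termination visit only where it is possible.

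**Working it through.** **Inputs**

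- Maximum use: 15 g per day, 105 g per week (Protocol 6.2).
- Kit size: 240 g, dispensed at Day 1 and Day 15 (Protocol 6.2, Table 1–1).
- Weekly average = total grams / duration × 7 (SAP 4.5.1).
- Duration = last-dose date − first-dose date + 1 (SAP 6.2.4).
- Assumed for illustration: constant daily use, and 14 exposure days in the first interval (Visit 3 on its nominal day).

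**The plan's own figure.** 15 g/day × 7 = 105 g/week, as stated.

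**When the rule works and when it does not**

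1. Visit 4, Visit 5 or early termination performed and the kit returned: the total is complete.
2. One of these visits performed without the kit, so that the amount is missing: the total is set to missing. A phone or video visit (Protocol 10.5) counted as performed has the same effect. There is no understatement.
3. None of these visits performed, and the last-dose date falls at about Visit 3: grams and days both cover the first interval. There is little or no understatement.
4. None of these visits performed, and the last-dose date is later than Visit 3: the total holds first-interval grams only and the duration covers more. The weekly average is understated.

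**Size in case 4.** With daily use u and D exposure days, the reported value is (14u/D) × 7 and the true value is 7u. The ratio is therefore 14/D.

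| Exposure days D | Reported/true = 14/D |
|---|---|
| 14 | 1.00 |
| 18 | 0.78 |
| 20 | 0.70 |
| 21 | 0.67 |
| 25 | 0.56 |
| 28 | 0.50 |

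Examples:

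- At 10 g/day, 140 g are recorded for the first interval and true use is 70 g/week. Last dose on Day 25: 140/25 × 7 = 39.2 g/week (44% low). Last dose on Day 20: 140/20 × 7 = 49.0 g/week (30% low).
- At 15 g/day over 28 days, 210/28 × 7 = 52.5 g/week against a true 105.

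**Effect on an arm mean.** The documents give no frequency. Assume that 1–3% of an arm falls in case 4, that these subjects have average use, and that the understatement is 30–50%. The mean then falls by between 0.01 × 0.30 = 0.3% and 0.03 × 0.50 = 1.5%.

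**With matched periods.** The 10 g/day subject gets 140/14 × 7 = 70 g/week, which is the true rate.

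**The case against.** The strongest case against is that this is a rare corner of a descriptive table.

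- **Two conditions must coincide.** Every return visit after Visit 3 must be missed, and a last-dose date well past Visit 3 must still be known. The paper diary comes back at the next visit (Protocol 6.5), so a subject never seen again leaves no diary for the second interval. Someone lost to follow-up is by definition out of contact (Protocol 7.3). The documents do not say how a last-dose date is set for such a subject; if it is placed near Visit 3, the error almost vanishes. This stands, and it keeps the point small. It does not remove it: a subject who withdraws and skips the remaining visits may still give a last-dose date by telephone for the end-of-treatment form.
- **The plan already reports by interval.** SAP 4.5.1 also presents amounts by visit interval, so the first-interval figure is correct and sits beside the total. Accountability listings would show an unreturned kit. This also stands, but the total-period figure and the listed individual value remain wrong when the stated rule is followed exactly.
- **A reader might infer that any unreturned second kit produces the error.** The documents do not support that. A subject who attends a later return visit without the kit has a missing amount at a performed visit, and the existing rule sets the total to missing.
- **A reader might infer that the overdose summary is understated as well.** That is not shown. SAP 4.5.1 lists overdose separately, as use above 105 g within one week, in line with Protocol 6.8. Neither document compares the total-period average with 105 g or derives the overdose count from it.

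**Conclusion.** The point holds, narrowly. When no return visit is performed after Visit 3 and the last-dose date is later, SAP 4.5.1 keeps a one-interval total and divides it by a longer exposure. At constant use and with Visit 3 on its nominal day, the individual weekly average is 30% low at 20 days, 44% low at 25 and 50% low at 28. Halving is the end of that range, not the typical case.

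The shift in arm means, roughly 0.3–1.5%, rests wholly on the assumed 1–3% frequency and on average use among those affected. Nothing in the documents indicates a difference between arms. The first-interval summary is unaffected, no efficacy test is touched, and no conclusion of the trial would change. This is a minor correction, worth making because the rule as written gives a wrong value and the remedy is short.

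**What to change.** In SAP 4.5.1, make two changes:

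1. Set the total amount to missing when any dispensed kit has no recorded amount, whether or not the return visit was performed.
2. Compute the total-period weekly average from the grams of those intervals where the amount is known, divided by the exposure days of the same intervals, times 7. State that this average can be reported even when the total is missing.

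The SAP already collects grams by visit interval and defines exposure days within an interval, so no new data are needed. The cost is about one sentence in the SAP and a small change in programming. The downside is that a few totals become missing, so the number of subjects behind the total and behind the average should be shown.
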